## **ATTR-CM**

ATTR-CM occurs when the amyloid fibrils infiltrate the myocardium, leading to diastolic dysfunction progressing to, heart failure, restrictive cardiomyopathy, and death. ATTR-CM, also known as familial amyloid cardiomyopathy (FAC), is a late-onset disease with symptoms typically occurring in patients over 60 years old. This disease can be inherited as an autosomal dominant trait caused by mutation in the TTR gene (commonly the Val122Ile mutation which occurs with high frequency [prevalence of 3.9%] in African-Americans); however, a mutation in TTR gene is not a pre-requisite for developing ATTR-CM. In the elderly, wild-type (normal) TTR may become structurally unstable resulting in deposition of amyloid fibrils primarily in heart tissue and leading to restrictive cardiomyopathy and heart failure.

Wild-type ATTR amyloidosis (previously known as senile systemic amyloidosis (SSA) or senile cardiac amyloidosis, is diagnosed based on positive bone scintigraphy (Perugini grade  $\geq 2$ ) or confirmed ATTR amyloid by tissue biopsy and immunohistochemical staining, and characteristic echocardiographic abnormalities in the absence of a TTR gene mutation and a plasma cell dyscrasia. The clinical presentation of

wild-type ATTR amyloidosis is similar to variant ATTR-CM, with the disease primarily affecting elderly males.

Combined heart and liver transplantation is a treatment option for ATTR-CM, however is limited by organ availability and significant patient co-morbidity.

Tafamidis is currently the only approved treatment for ATTR-CM with approvals in a growing number of countries worldwide including but not limited to: Japan (March 2019) for tafamidis meglumine 80 mg daily in patients with wild-type and variant forms of ATTR-CM; the US (May 2019) for tafamidis meglumine 80 mg daily and tafamidis 61mg daily for the treatment of the cardiomyopathy of wild-type or hereditary transthyretin-mediated amyloidosis in adults to reduce cardiovascular mortality and cardiovascular-related hospitalization; and the EU (February 2020) as a line extension to tafamidis 61 mg daily for the treatment of wild-type or hereditary transthyretin amyloidosis in adult patients with cardiomyopathy.

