## 11. MANAGEMENT AND REPORTING OF ADVERSE EVENTS/ADVERSE REACTIONS FOR TAFAMIDIS-TREATED SUBJECTS

### 11.1. Requirements

The table below summarizes the requirements for recording safety events in the THAOS electronic data record and for reporting safety events on the non-interventional study (NIS) adverse event monitoring (AEM) Report Form to Pfizer Safety. These requirements are delineated for 3 types of events: (1) serious adverse events (SAEs); (2) non-serious AEs (as applicable); and (3) scenarios involving drug exposure, including exposure during pregnancy (EDP), exposure during breast feeding, medication error, overdose, misuse, extravasation, and occupational exposure. These events are defined in the section “[Definitions of Safety Events](#)”

Safety event	Recorded in the THAOS electronic data record	Reported on the NIS AEM Report Form to Pfizer Safety within 24 hours of awareness
SAE	All	All
Non-serious AE	All	None
Scenarios involving exposure to a drug under study, including EDP, exposure during breastfeeding, medication error, overdose, misuse, extravasation; lack of efficacy; and occupational exposure	All (regardless of whether associated with an AE), except occupational exposure	All (regardless of whether associated with an AE)

For each AE, the investigator must pursue and obtain information adequate both to determine the outcome of the AE and to assess whether it meets the criteria for classification as a SAE (see section “[Serious Adverse Events](#)” below).

Safety events listed in the table above must be reported to Pfizer within 24 hours of awareness of the event by the investigator **regardless of whether the event is determined by the investigator to be related to tafamidis**. In particular if the SAE is fatal or life-threatening, notification to Pfizer or its designated representative must be made

immediately, irrespective of the extent of available event information. This timeframe also applies to additional new (follow-up) information on previously forwarded safety event reports. In the rare situation that the investigator does not become immediately aware of the occurrence of a safety event, the investigator must report the event within 24 hours after learning of it and document the time of his/her first awareness of the events.

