**Table 1 Summary of ongoing tafamidis safety concerns to be addressed in THAOS**

Level of Risk or Missing Information	Specific Concerns
Important potential risks	Hepatotoxicity Reproductive and developmental toxicity and lactation Changes in thyroid function, particularly in pregnant women
Important missing information	Safety and efficacy in patients with ATTR-PN variants other than Val30Met (B3461029 substudy) CCI █ Patients with severe hepatic impairment

Note: The important identified risks (Urinary tract infections, Diarrhea, Upper abdominal pain and Vaginal infections); important potential risks (Hypersensitivity reactions); and missing information (Safety and efficacy in elderly patients and Longer-term safety) have been removed from the list of ongoing safety concerns from the tafamidis EU Risk Management Plan (RMP) Update (v 9.3), approved on 17 February 2020 and therefore will not be addressed in the final clinical study report (CSR) for THAOS.

All AE/SAE data will be collected for patients treated with commercially available tafamidis; patients receiving tafamidis as part of their participation in an open-label clinical study will have AE/SAE data collection through the open-label clinical study; reporting of Health Events of Interest will be available for patients not treated with tafamidis.

All visits are intended to be outpatient visits. Table 2 presents the data collected throughout a patient's participation in THAOS per the case report form (CRF). All assessments listed in Table 2 are recommended, but not required and will be determined by the investigator.

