## **8 STATISTICAL METHODOLOGY AND STATISTICAL ANALYSES**

### **8.1 STATISTICAL METHODS**

The key objectives of the survey are to better understand the natural history of ATTR (hereditary and wild-type forms) and the progression of disease in this patient population. Analysis of clinical outcomes will be conducted on all enrolled patients with available data. Outcomes will be examined separately for the untreated and tafamidis treated sets, as well as for appropriate subgroups within these set. Outcomes will include results of the key clinical, functional and QoL assessments used to define progression of disease.

Data will be summarized descriptively.

Continuous variables will be summarized using descriptive statistics ie, number of non-missing values and number of missing values [ie, n (missing)], mean, median, standard deviation (SD), minimum, maximum and 10th and 90th percentile.

Qualitative variables will be summarized by frequency counts and percentages. Unless otherwise specified, the calculation of proportions will be based on non-missing values.

In case the analysis refers only to certain visits, percentages will be based on the number of patients still present in the study at that visit, unless otherwise specified. Sample size in a subgroup needs to be at least 10 in order to have sufficient data to provide descriptive statistics, listings will be provided for smaller subgroups.

Kaplan-Meier estimates (product-limit estimates) will be presented including the median time with two-sided 95% confidence intervals (CIs), if the number of events are at least 5.

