### **Exposure**

Duration of exposure (in years) among patients receiving tafamidis while enrolled in THAOS will be summarized (excluding time when the patient was part of clinical trial or Compassionate Use/Early Access Program) by starting dose using the tafamidis treated set by phenotype at enrollment and overall, CCI [REDACTED] and either predominantly cardiac or mixed phenotype at enrollment, tafamidis treated set for patients who had severe hepatic impairment at baseline, tafamidis treated set by liver transplantation status (liver transplant prior to first dose of tafamidis/liver transplant after the first dose of tafamidis/no liver transplant).

Additionally the duration of treatment with 20 mg and 61 mg/80 mg will be summarized separately for patients with off label use.

The duration of exposure (in years) will be calculated as:

Sum of all non-missing days when tafamidis was taken (excluding days of other clinical trial/compassionate use participation) / 365.25

Summary of exposure-adjusted Incidence rates (per patient-year) AEs and SAE for Treatment Emergent Adverse events (All causalities) and mortality for tafamidis treated set will be provided.

A separate listing will be provided for duration of exposure listing for patients who switched from 61/80 mg to 20 mg.

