### Adverse Events & Serious Adverse Events

All adverse events will be coded according to the latest Medical Dictionary for Regulatory Activities (MedDRA) version at the time of analysis.

Adverse events (all causality and treatment-related) will be summarized by severity and starting dose using the tafamidis treated set by phenotype at enrollment and overall, CCI [REDACTED] and either predominantly cardiac or mixed phenotype at enrollment, tafamidis treated set for patients who had severe hepatic impairment at baseline, tafamidis treated set by liver transplantation status (liver transplant prior to first dose of tafamidis/liver transplant after the first dose of tafamidis/no liver transplant).

Separate summaries will be provided for all AEs, treatment related AEs, all SAEs, treatment related SAEs, AEs leading to dose reduction, AEs leading to withdrawal of tafamidis (temporarily or permanently, or delayed) and AEs leading to tafamidis dose interruptions.

Listings will be provided for adverse events corresponding to all enrolled patients and for patients with off-label usage of tafamidis. A separate listing of SAEs will also be provided for tafamidis treated set.

The following AE summary tables will be provided corresponding to some of the important potential risks using the tafamidis treated set.

- For **hepatotoxicity** using the search criteria: MedDRA SMQ (Standardized MedDRA Query) [Broad and narrow] Drug related hepatic disorders – comprehensive search. The derivations and conventions related to the search criteria will follow the programming specifications done in the Periodic Safety Update Report (PSUR) 12 for tafamidis.
- For **reproductive and developmental toxicity and lactation**:
  - MedDRA SMQ (Broad and narrow): Congenital, familial and genetic disorders; Foetal disorders; Neonatal disorders, Neonatal exposures via breast milk.
  - MedDRA Preferred terms (PTs): Exposure during pregnancy, Exposure via father, Foetal exposure during delivery, Foetal exposure during pregnancy, Foetal exposure timing unspecified, Maternal exposure before pregnancy, Maternal exposure during delivery, Maternal exposure during pregnancy, Maternal exposure timing unspecified, Drug exposure before

- pregnancy, Exposure via breastmilk, Maternal drug affecting foetus, Maternal exposure during breastfeeding
- The derivations and conventions related to the search criteria will follow the programming specifications done in the PSUR 12 for tafamidis.

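### The reproductive and lactation risk table has no exposed-pregnancy or breastfeeding denominator and mixes exposure terms with outcome terms, so its percentages cannot be read as a risk per exposure

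*SAP*

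**What the plan says.** SAP Table 1 lists three ongoing important potential risks. Two bear on pregnancy: "Reproductive and developmental toxicity and lactation" and "Changes in thyroid function, particularly in pregnant women". The third is hepatotoxicity.

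For these risks SAP 8.2.6 (Adverse Events & Serious Adverse Events) says: "The following AE summary tables will be provided corresponding to some of the important potential risks using the tafamidis treated set". The reproductive search combines MedDRA queries for congenital, foetal and neonatal disorders with a list of preferred terms, most of which record only that an exposure took place (in pregnancy, at delivery, through breast milk, or via the father). The thyroid table is a single thyroid-dysfunction query with no pregnancy split. The hepatotoxicity table is likewise specified only for the treated set.

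On presentation, SAP 8.1 says "Qualitative variables will be summarized by frequency counts and percentages" and "Unless otherwise specified, the calculation of proportions will be based on non-missing values". Nothing in 8.2.6 specifies otherwise for these tables. The reference there to PSUR 12 concerns the search criteria. The Exposure part of 8.2.6 adds AE rates per patient-year, also on the treated set.

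The treated set (SAP 5.3) has no sex or age limit. No legible subgroup in SAP 5.4 and no legible column in the 8.2.8 summary covers women, exposed pregnancies, births or breastfeeding. Some headings are blacked out, but where 8.2.6 uses a redacted group it pairs it with cardiac or mixed phenotype, which does not suggest a pregnancy group.

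In the Protocol 11.1 table, the row beginning "Scenarios involving exposure to a drug under study, including EDP" requires exposures in pregnancy and breastfeeding to be recorded in the THAOS data record whether or not an AE occurred.

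**The concern.** A foetal or neonatal outcome can arise only from a pregnancy, and a lactation outcome only from a breastfed infant. The treated set is mostly defined by other things. Protocol 7.1 describes wild-type disease "with the disease primarily affecting elderly males", while Val30Met polyneuropathy usually begins in the third to fourth decade, so the set mixes patients who can and cannot have an exposed pregnancy. A percentage over that mixture reflects the demographic make-up of the registry more than any hazard of the drug in pregnancy.

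Pooling the terms adds a second problem. An exposure term says that a pregnancy or breastfeeding exposure happened; an outcome term says that something went wrong. One total over both cannot be interpreted, and it places what should be the denominator inside the numerator.

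The SAP supports the final report of a designated post-authorisation safety study, and Table 1 commits that report to addressing this risk. As specified, the table does not give a reader a usable estimate.

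**Working it through.** The documents state no treated count, pregnancy count or event count, so there is no planned figure to reproduce. The check has two parts.

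**Which denominator follows from the text**

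1. Analysis set: tafamidis treated (SAP 8.2.6).
2. Statistic: counts and percentages over non-missing values unless specified otherwise (SAP 8.1).
3. Exception for these tables: none in 8.2.6, and no matching subgroup in 5.4 or column in 8.2.8.
4. Result: outcomes over all treated patients. This is inferred from steps 1 to 3; the SAP does not write it out.

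**How large the effect could be**

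Let N be treated patients, P tafamidis-exposed pregnancies and x adverse outcomes. All three are assumptions.

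- Percentage as planned: x/N
- Percentage per exposed pregnancy: x/P
- Dilution: (x/P) / (x/N) = N/P, whatever x is

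For N from 500 to 3,000 and P from 5 to 40:

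- smallest dilution: 500/40 = 12.5
- largest dilution: 3,000/5 = 600
- largest with P of at least 10, where the SAP would allow a percentage: 3,000/10 = 300

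Example with P = 20 and x = 2 (exact Clopper-Pearson 95% intervals):

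| Denominator | Proportion | 95% CI | Dilution |
|---|---|---|---|
| 20 exposed pregnancies | 2/20 = 10.0% | 1.2 to 31.7% | none |
| 500 treated | 2/500 = 0.40% | 0.05 to 1.44% | 25 |
| 1,500 treated | 2/1,500 = 0.13% | 0.02 to 0.48% | 75 |
| 3,000 treated | 2/3,000 = 0.07% | 0.01 to 0.24% | 150 |

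Example with no outcomes: the upper 95% limit is 1 − 0.025^(1/n). For n = 20 pregnancies it is 16.8%. For n = 2,000 treated patients it is 0.18%. The same zero therefore excludes very different risks depending on the denominator.

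The direction is certain whenever exposed pregnancies are fewer than treated patients. Only the size is assumed. The counts themselves do not change.

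**The case against.** The strongest reply is that 8.2.6 names an analysis set, not a denominator, and that much of the information will be visible anyway. Counts accompany percentages. If the table is shown by preferred term, exposed cases and outcomes appear as separate lines that a careful reader could relate. The SAP also plans AE listings for all enrolled patients and an SAE listing for the treated set, and Protocol 11.6.1 puts adverse pregnancy outcomes through SAE reporting. Exposed pregnancies also go to sponsor safety and to the enhanced pregnancy surveillance programme (TESPO), with questionnaires at 6 and 12 months after birth. All analyses are descriptive.

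This rightly lowers the severity. It does not remove the gap: the SAP does not say that the lines will be separated, sets no per-pregnancy proportion, and does not bring TESPO data into this report. The paternal-exposure term in the search does not make treated men a suitable base either, since Protocol 11.6.1 defines exposure during pregnancy as maternal.

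Three stronger readings are tempting and not supported:

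- *That the thyroid table has the wrong denominator.* Thyroid dysfunction can occur in any treated patient, and Table 1 stresses pregnant women without restricting the risk to them. Only a pregnant subset is missing.
- *That transplant recipients' liver events go unseparated.* The general AE summaries in 8.2.6 are already split by transplant status, and 8.2.8 marks those columns. Only the hepatotoxicity query table is not repeated by stratum.
- *That the reported risks will look close to zero and falsely reassure.* Without counts this cannot be shown, and the counts and listings partly offset it.

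**Conclusion.** The point holds for the reproductive, developmental and lactation table. It lacks a denominator of exposed pregnancies or breastfeeding exposures and pools exposures with harms, so its percentages cannot answer the question posed in SAP Table 1. The same applies to any patient-year rate for these terms on the treated set.

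The conclusion rests on reading SAP 8.1 and 8.2.6 together, which is the natural but not the only possible reading. The dilution is N/P; the 12.5- to 600-fold range holds only under the assumed counts. The thyroid item is a missing subset, and the hepatotoxicity item a convenience for the reader. This is a change that should be made, short of a defect that would invalidate the report.

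**What to change.** In SAP 8.2.6:

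1. Split the reproductive and lactation search into exposure terms and outcome terms, and never total across the two.
2. Report pregnancy outcomes as n/N recorded tafamidis-exposed pregnancies, and lactation outcomes as n/N recorded breastfeeding exposures, each with an exact 95% interval. Where N is below 10, give a case listing, in line with the minimum-size rule in 8.1.
3. Keep the treated set for overall thyroid events and add a row, or a listing if fewer than 10, for women with an exposed pregnancy.
4. As a secondary addition, repeat the hepatotoxicity query table by the liver-transplant strata already defined for treated patients in 5.4.

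The cost is SAP wording and some reprogramming. Protocol 11.1 already requires the exposures to be recorded, so the denominators should be countable. Whether each outcome can be linked to its pregnancy or infant needs checking first, because SAP Table 2 shows no pregnancy or infant form. Denominators will be small and intervals wide, which is an honest picture of what the registry can show.

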In the case of a live birth, the structural integrity of the neonate can be assessed at the time of birth. In the event of a termination, the reason(s) for termination should be specified and, if clinically possible, the structural integrity of the terminated fetus should be assessed by gross visual inspection (unless pre-procedure test findings are conclusive for a congenital anomaly and the findings are reported).

If the outcome of the pregnancy meets the criteria for an SAE (eg, ectopic pregnancy, spontaneous abortion, intrauterine fetal demise, neonatal death, or congenital anomaly [in a live born, a terminated fetus, an intrauterine fetal demise, or a neonatal death]), the procedures for reporting SAEs should be followed.

Additional information about pregnancy outcomes that are reported as SAEs follows:

- Spontaneous abortion includes miscarriage and missed abortion;
- Neonatal deaths that occur within 1 month of birth should be reported, without regard to causality, as SAEs. In addition, infant deaths after 1 month should be reported as SAEs when the investigator assesses the infant death as related or possibly related to exposure to investigational product.

Additional information regarding the EDP may be requested. Further follow-up of birth outcomes will be handled on a case-by-case basis (eg, follow-up on preterm infants to identify developmental delays).

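### The SAP's search for reproductive and developmental toxicity names no term for spontaneous abortion or ectopic pregnancy, two of the five pregnancy outcomes that the protocol names as SAEs

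*SAP*

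**What the plan says.** SAP Table 1 keeps "Reproductive and developmental toxicity and lactation" as one of three ongoing important potential risks. In section 8.2.6, under adverse events, the SAP introduces the risk-specific outputs: "The following AE summary tables will be provided corresponding to some of the important potential risks using the tafamidis treated set".

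For this risk the search has two parts. The first is a set of query headings: "MedDRA SMQ (Broad and narrow): Congenital, familial and genetic disorders; Foetal disorders; Neonatal disorders, Neonatal exposures via breast milk". The second is a list of preferred terms that begins "Exposure during pregnancy, Exposure via father, Foetal exposure during delivery, Foetal exposure during pregnancy, Foetal exposure timing unspecified" and ends "pregnancy, Exposure via breastmilk, Maternal drug affecting foetus, Maternal exposure during breastfeeding" (the first word of that last quote closes a term for drug exposure before pregnancy). The SAP adds that derivations and conventions for the search follow the programming specification of PSUR 12, which is not among the documents.

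Protocol 11.6.1 applies SAE reporting to pregnancy outcomes that meet SAE criteria and gives as examples "ectopic pregnancy, spontaneous abortion, intrauterine fetal demise, neonatal death, or congenital anomaly". It then clarifies: "Spontaneous abortion includes miscarriage and missed abortion".

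**The concern.** A reader of the final report who wants to know what happened in pregnancies exposed to tafamidis will go first to the table made for this risk. Pregnancy loss is among the outcomes that such a table should show. The search as written retrieves exposure records and some fetal and neonatal events, but it names nothing for a miscarriage or an ectopic pregnancy. The table could then list exposed pregnancies with no losses beside them, and a reader could take the blank as absence of events. The risk is one of those that this post-authorisation safety study is meant to characterise for the EMA, so the dedicated table should match the outcomes that the protocol asks sites to report.

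**Working it through.** The plan states no figure here and no calculation applies. The check sets the protocol's outcomes against the SAP's search terms.

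**Inputs**
- Outcomes: the five named in Protocol 11.6.1.
- Query headings: the four in SAP 8.2.6 (congenital, familial and genetic; foetal; neonatal; neonatal exposure via breast milk).
- Preferred terms: I count 13 in SAP 8.2.6. Twelve are exposure labels (in pregnancy, via father, during delivery, before pregnancy, via breast milk or breastfeeding, timing unspecified). The other is the term for a maternal drug affecting the foetus. None is an abortion, miscarriage, stillbirth, fetal death or ectopic term.

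**Match**

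| Outcome in Protocol 11.6.1 | Heading in SAP 8.2.6 | Outcome-specific preferred term | Result |
|---|---|---|---|
| Congenital anomaly | Congenital, familial and genetic | none | covered by heading |
| Neonatal death | Neonatal | none | covered by heading |
| Intrauterine fetal demise | Foetal, if it holds the term | none | cannot be determined |
| Spontaneous abortion, with miscarriage and missed abortion | none | none | not named |
| Ectopic pregnancy | none | none | not named |

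Count: 2 covered + 1 undetermined + 2 not named = 5.

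**What the table would show.** Protocol 11.1 has exposure in pregnancy recorded whether or not an AE occurs, and all SAEs recorded as well. Protocol 11.6.1 has the pregnancy followed to its outcome. A treated patient who miscarries can therefore have two records: an exposure term and a loss term. The search names the first and not the second. On the stated terms, the table would show this patient as an exposure only.

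**Where else the event appears.** SAP 8.2.6 also provides summaries of all AEs and all SAEs in the treated set, an AE listing for all enrolled patients and an SAE listing for the treated set. A loss reported as an SAE within the SAP's period for the treated set (to 28 days after the last dose) would be found there.

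**The case against.** The strongest reply is that non-capture has not been demonstrated. What the table retrieves depends on the contents of the four queries, searched both broadly and narrowly, and on the PSUR 12 specification. None of these is in the documents, and loss terms may sit in either place. This stands as a limit on certainty: the gap is shown only on the face of the SAP. It does not remove the point. The SAP cites PSUR 12 for how the search criteria are derived and programmed, with the same sentence after the hepatotoxicity and thyroid searches, whose queries are also written out. On that wording, PSUR 12 does not extend the list. If it does hold loss terms, the SAP's list is incomplete and should state them.

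The second reply is that nothing is lost. Such outcomes are reported as SAEs and reach the general summaries and listings. Pregnancies during tafamidis treatment also go to the sponsor on the EDP supplemental form and through the enhanced pregnancy surveillance programme (Protocol 11.6.1). This also stands. A reader might infer that the final report as a whole would under-report pregnancy loss; the documents do not support that. The weakness is that a reader would have to assemble this risk from general outputs, when a dedicated table exists to spare them that.

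The third reply is that materiality is unknown. The documents give no number of pregnancies or losses, and all analyses are descriptive. That is correct, and it is why the point concerns the search definition and not the size of any bias.

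**Conclusion.** The point holds for the risk-specific table. Two of the five outcomes that Protocol 11.6.1 names as SAEs, spontaneous abortion and ectopic pregnancy, have no heading or preferred term in the SAP 8.2.6 search, and a third, intrauterine fetal demise, is undetermined. It would be wrong to extend this to all pregnancy outcomes, since neonatal death and congenital anomaly do have headings.

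The conclusion assumes that the four queries contain what their titles say and that PSUR 12 adds no terms. If either assumption fails, some or all of the gap closes in practice, but the SAP would still not tell its reader so. The stated search rule should be corrected; the underlying data are not affected.

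**What to change.** In SAP 8.2.6, add explicit search terms for each outcome named in Protocol 11.6.1: at least spontaneous and missed abortion, ectopic pregnancy and fetal death. Check the matching query and term names in the MedDRA version used for the analysis and against the PSUR 12 specification. If PSUR 12 already includes such terms, write them into the SAP so that the definition stands alone.

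In the table, show pregnancy outcomes in a block separate from exposure-only terms, so that exposed pregnancies and their outcomes can be read side by side.

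The cost is a few search terms and one layout change in a single table, with no new data. If the existing queries already contain some of the added terms, naming them does no harm provided each event is counted once.
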